5.2.5 Prior and Concomitant Therapy

All investigator terms for medications recorded in the eCRF will be coded to an 11-digit code using the World Health Organization Drug Dictionary (WHO DD) (Mar 2020). The number (percentage) of subjects who took prior and concomitant medications will be summarized on the Safety Analysis Set by subgroup and overall, Anatomical Therapeutic Chemical (ATC) class, and WHO DD preferred term (PT). Prior medications will be defined as medications that stopped before the first dose of study drug. Concomitant medications will be defined as medications that (1) started before the first dose of study drug and were continuing at the time of the first dose of study drug, or (2) started on or after the date of the first dose of study drug up to the date of the last dose. All medications will be presented in subject data listings.

Prior and concomitant medications will be summarized by cognitive and non-cognitive medications categorized under DLB and PDD medications, all other medications not categorized under DLB and PDD medications will be summarized separately.

Restricted medications taken at baseline, and changes in restricted medications taken at any time post baseline will be summarized separately. Prohibited medications will be summarized separately if numbers allow.

Medications taken within the 4-week Follow-Up Period will also be listed.

5.2.6 Treatment Compliance

Percent compliance will be calculated for the Safety Analysis Set as follows:

Compliance = (Total number of capsules dispensed – Total number of capsules returned – Total Number of capsules lost) x 100% / Planned Total number of capsules to be taken

Overall compliance with study medication will be summarized using descriptive statistics (median, mean, standard deviation, minimum, maximum, and number of subjects with non-missing data) for each subgroup. Subjects will also be categorized by compliance criteria <50%, $\geq 50\%$ to <80%, $\geq 80\%$ to $\leq 100\%$, >100% to $\leq 120\%$, >120% and missing. The maximum of planned total number of capsules to be taken will be 168

5.3 Data Analysis General Considerations

5.3.1 Pooling of Centers

This is a multi-center study conducted in United States and Canada. Due to the small number of subjects per site and location of sites, subjects from all centers will be pooled for all summaries and analyses.

5.3.2 Adjustments for Covariates

Where statistical analysis models are used, the baseline of the variable will be included as a covariate.

5.3.3 Multiple Comparisons/Multiplicity

Not applicable.

5.3.4 Examination of Subgroups

The primary subject subgroups will be compared for all data:

- DLB without amyloid copathology versus DLB with amyloid copathology, and PDD without amyloid copathology versus PDD with amyloid copathology). Amyloid copathology is defined by the plasma A β 42/40 ratio: with <0.092, without ≥ 0.092 .
- The above subgroups will be combined to compare with amyloid vs without amyloid copathology, DLB without amyloid vs PDD without amyloid, and DLB with amyloid vs PDD with amyloid).

The demography, MoCA and some of the PD endpoints will be presented by the subgrouping as column headers instead of the amyloid copathology:

- Plasma p-tau181/A β (1-42) (<0.043, ≥ 0.043), by DLB, PDD and Overall

- CSF amyloid status (CSF A β 42/40 <0.0571, CSF A β 42/40 \geq 0.0571), by DLB, PDD and Overall
- Genotype classification (ApoE4 positive or negative), by DLB, PDD and Overall
- Plasma p-tau181 (<2.2, \geq 2.2), by DLB, PDD and Overall
- CSF p-tau181 (<52.8, \geq 52.8), by DLB, PDD and Overall
- CSF p-tau181/ A β 42 (<0.083, \geq 0.083), by DLB, PDD and Overall
- CSF total tau/A β 42 (<0.637, \geq 0.637), by DLB, PDD and Overall
- If data permits, combinations of the above overall for DLB+PDD,
 - a) plasma A β 42/40 <0.092 and ApoE4 positive, A β 42/40 <0.092 and ApoE4 negative, A β 42/40 \geq 0.092 and ApoE4 negative, A β 42/40 \geq 0.092 and ApoE4 positive.
 - b) CSF A β 42/40 <0.0571 and ApoE4 positive, CSF A β 42/40 <0.0571 and ApoE4 negative, CSF A β 42/40 \geq 0.0571 and ApoE4 negative, CSF A β 42/40 \geq 0.0571 and ApoE4 positive.
- Other biomarkers, to be determined if data permit (all cutpoints TBD).

Additional subgroup analyses may also be conducted, if deemed appropriate.

Where subgroups are small, summaries and analyses will be produced, caution will be used in the interpretation of those subgroups.

5.3.5 Handling of Missing Data, Dropouts, and Outliers

5.3.5.1 Efficacy

For the efficacy endpoints, there will be no imputation of missing value.

Post-ED data will be included in all the analyses.

5.3.5.2 Safety

The methods for handling missing start and end dates are described in standard Eisai Study Data Tabulation Model (SDTM) Domain Mapping Specifications Template and documented in SDTM+ specification.

All the listings will display the original missing values.

5.3.6 Other Considerations

Not Applicable.

5.4 Efficacy Analyses

5.4.1 Primary Efficacy Analyses

Not applicable.

5.4.2 Secondary Efficacy Analyses

Not applicable.

5.4.3 Other Efficacy Analyses

Exploratory efficacy analyses are described in Section 5.8 Exploratory Analyses.

5.5 Pharmacokinetic, Pharmacodynamic, Pharmacogenomic, and Other Biomarker Analyses

E2027 plasma and CSF concentrations were obtained during the dosing period (Week 9 for plasma for biomarkers, Weeks 6, 9 and 12 for plasma for PK and Screening and Week 9 for CSF). Details of the analysis methods for population PK/PD modeling will not be described in this SAP but will be described in a separate analysis plan.

5.5.1 Pharmacokinetic Analyses

The Safety Analysis Set will be used for E2027 concentration listings and for summaries of E2027 concentrations in plasma and CSF by dose and day.

A population PK approach will be used to characterize the plasma PK of E2027. For this approach, PK data from this study will be pooled with relevant data from Phase 1 and 2 studies. As appropriate, the effect of covariates on the PK of E2027, such as baseline characteristics/demographics will be evaluated. Derived exposure parameters such as steady state area under the concentration time curve or average concentration of E2027 and other derived parameters may be calculated from the final PK model using the individual posterior estimates of the PK parameters and dosing history. The details will be described in the separately prepared analysis plan.

5.5.2 Pharmacodynamic, Pharmacogenomic, and Other Biomarker Analyses

Pharmacodynamic Analyses

The PD Analysis Set will be used for the summaries and analyses of CSF and plasma PD biomarkers. The percentage change from baseline in CSF cGMP at 9 weeks of treatment will be analyzed to compare different subject subgroups (DLB without amyloid copathology vs DLB with amyloid copathology, and PDD without amyloid copathology vs PDD with amyloid copathology). Secondary comparisons will be: total (DLB+PDD) without amyloid vs with amyloid, DLB without amyloid vs PDD without amyloid, and DLB with amyloid vs PDD with amyloid.

Analyses, comparing the different subgroups, of the percentage change from baseline in CSF cGMP will be performed using an analysis of covariance, where baseline CSF cGMP will be included as a covariate. The least square (LS) means, LS mean subgroup differences and 95% CIs will be presented.

The change from baseline in CSF cGMP at 9 weeks of treatment will also be analyzed. Other CSF and plasma PD biomarkers (CSF amyloid, plasma p-tau181, CSF p-tau181, plasma neurogranin, plasma neurofilament, CSF neurogranin, CSF neurofilament, etc) may be analyzed similarly, if appropriate.

The CSF and plasma PD biomarkers (both percentage change and change from baseline at 9 weeks) will be summarized by subgroups, as defined in section 5.3.4.

Summaries and figures will be produced exploring the relationships between CSF and plasma PD biomarkers and the efficacy endpoints. If data permit, the relationship between CSF and plasma PD biomarkers compared to each efficacy endpoint (MoCA, WAIS-IV DSC, CIBIC-Plus, CGIC, CFI, MMSE, NPI [NPI-12, NPI-10, NPI-4 and NPI-D, and each subscore], SAPS-PD and FAQ) and MDS-UPDRS-III will be explored using correlation analysis. The association between individual CSF/plasma biomarker concentration data and individual efficacy data within each subgroup (DLB without amyloid copathology vs DLB with amyloid copathology; PDD without amyloid copathology vs PDD with amyloid copathology; total (DLB+PDD) without amyloid vs with amyloid; DLB without amyloid vs PDD without amyloid; and DLB with amyloid vs PDD with amyloid) will be examined through scatter plots. The scatter plots including the Pearson correlation coefficient and Spearman correlation coefficient will be produced for each amyloid subgroup for both percentage change from baseline and change from baseline (as appropriate) in CSF and plasma PD biomarkers after 9 weeks of treatment and change from baseline at 12 weeks of treatment for the efficacy endpoints. Correlations against CSF and plasma biomarkers at baseline compared to change from baseline at 12 weeks of treatment for the efficacy endpoints may also be explored, by subgroups.

If appropriate, relationships amongst plasma biomarkers and CSF biomarkers (including cGMP) at baseline and after treatment will be explored using summaries, correlation analysis and scatter plots.

Pharmacogenomic Analyses

The percentage change in CSF cGMP at 9 weeks, change in CSF cGMP at 9 weeks and other CSF and plasma PD biomarkers will be summarized by ApoE4 status, using the PD Analysis Set. Other pharmacogenomic data will be summarized similarly.

Pharmacodynamic/Pharmacokinetic Analyses

The correlation amongst plasma and CSF exposure to E2027 and the various efficacy and biomarker endpoints will be explored graphically. The details will be described in the separately prepared analysis plan.

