4 DETERMINATION OF SAMPLE SIZE

Assuming the standard deviation of percentage change from baseline in CSF cGMP at Week 9 was 60, the sample size of 6 completers per subgroup (for 8 enrolled subjects per subgroup, assuming a 25% dropout rate), would have approximately 80% power to detect the difference in change from baseline of CSF cGMP of 100% between the DLB without amyloid copathology subgroup and the DLB with amyloid copathology subgroup. The analysis between the PDD without amyloid copathology subgroup and the PDD with amyloid copathology subgroup, also would have approximately 80% power to detect the difference in change from baseline of CSF cGMP of 100% (same assumptions as above). These sample size calculations illustrated the possible differences that could be seen between subgroups. However, without previous data on the differences between subgroups in CSF cGMP, these were for illustration only and it was not expected statistical significance would be reached with 6 subjects per subgroup.

The probability of observing a difference in percentage of CSF cGMP between 2 subgroups (DLB without amyloid copathology subgroup minus DLB with amyloid copathology subgroup, or PDD without amyloid copathology subgroup minus PDD with amyloid copathology subgroup) $\geq 30\%$ depends on the true difference between the 2 subgroups. If the true difference was 100%, there would be 97.8% probability that the observed difference was $\geq 30\%$. If the true difference was 60%, the probability was 80.7%. If the true difference was 10%, there would be 28.2% probability that the observed difference was $\geq 30\%$.

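### The pooled DLB+PDD amyloid comparison names baseline cGMP as its only covariate; the SAP should state one four-subgroup ANCOVA so that diagnosis is accounted for (minor)

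*SAP*

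**What the plan says.** SAP 5.5.2 makes the comparisons within DLB and within PDD the main ones, then adds: "Secondary comparisons will be: total (DLB+PDD) without amyloid vs with amyloid". It also adds DLB versus PDD within each amyloid stratum, so five comparisons are listed. The model is given once for all of them: "will be performed using an analysis of covariance, where baseline CSF cGMP will be included as a covariate". SAP 5.3.2 gives the general rule: "Where statistical analysis models are used, the baseline of the variable will be included as a covariate". SAP 5.3.4 describes how the pooled groups are formed: "The above subgroups will be combined to compare with amyloid vs without amyloid copathology".

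Diagnosis is not named as a factor or stratum for the pooled contrast in either document. The SAP also does not say whether the five comparisons come from one model with four subgroups or from a separate two-group model for each.

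Protocol 9.2 plans equal numbers in the four subgroups. Protocol 9.5.5 allows, but does not require, further enrolment when a subgroup has fewer than 6 subjects with 9 weeks of treatment and the second CSF sample. SAP 5.2.1 removes subjects with low compliance on PK results from the PD Analysis Set.

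**The concern.** Diagnosis is one of the two factors that define the enrolment quotas, and the SAP itself compares DLB with PDD. A programmer who follows the text literally could merge the cells by amyloid status and fit amyloid group plus baseline cGMP. If the two merged groups then contain different shares of DLB subjects, any DLB-PDD difference in cGMP response leaks into the amyloid contrast. If the shares are equal, the same difference goes into the residual and widens the reported interval.

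The pooled contrast has about 12 subjects per side against 6 for each main comparison, so readers will look at it. Protocol 7.3 says the results will guide the choice of subgroups for Phase 3.

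**Working it through.** **Inputs.** SD 60, 6 completers and 8 enrolled per subgroup, 25% dropout (SAP 4). Difference of interest 30 points (Protocol 9.2). Two-sided 5%, assumed from the 95% CIs. The DLB-minus-PDD difference in response given baseline, *g*, is not in the documents; I take 0 to 60 points as an assumed range. SD 60 is used as the residual SD. Cells are listed as DLB without / DLB with / PDD without / PDD with amyloid.

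**The plan's own figures.** n = 2 × (1.960 + 0.842)² × 60² / 100² = 5.65, so 6 per subgroup, and 6/0.75 = 8 enrolled. The SE of a two-cell difference is 60 × √(2/6) = 34.64. The chance of observing at least 30 is Φ((d − 30)/34.64), which is 97.8%, 80.7% and 28.2% for d = 100, 60 and 10. All match SAP 4. Power at 100 points is 82.3% by the normal approximation and 74.0% by a t-test.

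**Bias of a two-group pooled ANCOVA.** Bias = *g* × (DLB share without amyloid − DLB share with amyloid).

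| Cells | Share gap | Bias at g = 30 | Bias at g = 60 |
|---|---|---|---|
| 6/6/6/6 | 0 | 0 | 0 |
| 8/8/4/4 | 8/12 − 8/12 = 0 | 0 | 0 |
| 8/6/6/6 | 8/14 − 6/12 = 0.071 | 2.1 | 4.3 |
| 6/8/8/6 | 6/14 − 8/14 = −0.143 | −4.3 | −8.6 |
| 8/5/5/7 | 8/13 − 5/12 = 0.199 | 6.0 | 11.9 |

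The 6/8/8/6 layout is the worst case with every cell between 6 and 8.

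**How often shares differ.** With 8 enrolled per cell and independent 25% dropout, the exact binomial calculation gives unequal DLB shares with probability 0.91 (mean gap 0.09, 95th percentile 0.22). If every cell is topped up to at least 6, the probability is 0.70 (mean gap 0.04, 95th percentile 0.11). PK-based exclusion comes on top, and its pattern is unknown.

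**Interval width with 6 per cell.** Without diagnosis, the expected residual variance is 60² + *g*² × Σ*np*(1 − *p*)/(*N* − 3), where *p* is the DLB share in each amyloid group, *n* its size and *N* the total. Here Σ*np*(1 − *p*) = 6, with 21 error df.

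- g = 30: √(3600 + 900 × 6/21) = 62.1; half-width 2.080 × 62.1 × √(2/12) = 52.7.
- g = 60: √(3600 + 3600 × 6/21) = 68.0; half-width 57.8.
- Four-level model, 19 df, any g: 2.093 × 60 × √(2/12) = 51.3.
- g = 0 without diagnosis: 50.9.

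The two widths cross where 2.080 × √(3600 + *g*² × 6/21) = 2.093 × 60, at *g* of about 13 points. The crossing is at about 9 if diagnosis is added as a single term.

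**True precision with 6 per cell.** In a simulation (20,000 runs per setting) the sampling SD of the estimate was 25.0 in both models at g = 30, and 25.3 without versus 25.1 with the four-level factor at g = 60. The interval without diagnosis is conservative (coverage 95.6% and 96.9%) and the estimator itself is no less precise.

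**Main comparisons, if they would otherwise be separate two-group models.** Error df rise from 9 to 19 at 6 per cell. The half-width falls from 2.262 × 34.64 = 78.4 to 2.093 × 34.64 = 72.5, and power at 100 points rises from 72.9% to 78.2%.

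**The case against.** The strongest reply is that the fault is inferred from silence. SAP 5.3.2 says that baseline enters the model; it does not forbid other terms. A single ANCOVA across the subgroups, reporting LS means and their differences, fits the wording of SAP 5.5.2, and table shells and programming rules are in separate documents. This stands. The defect is that the text permits a two-group model, and the gain in df for the main comparisons counts only if separate models were intended.

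Two stronger readings are tempting, and neither is supported.

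- A reader might infer that unequal cells alone bias the pooled contrast. They do not: 8/8/4/4 gives zero bias for any *g*.
- A reader might infer that omitting diagnosis loses precision even with equal cells. Only the reported interval widens, and only once *g* passes roughly 9 to 13 points.

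The size is also open to challenge. SAP 4 says there are no previous data on subgroup differences in cGMP, and Protocol 9.2 treats DLB and PDD as two ends of one spectrum. Listing a DLB-PDD comparison is not evidence of a large difference. Full subgroups are closed at screening (Protocol 9.1.1.1), which limits crossed imbalance. With cells of 8/5/5/7, coverage without diagnosis was still about 95% in simulation at g = 30 and 60, because the wider interval offsets the bias. Finally, the main comparisons are made within diagnosis, so diagnosis cannot confound them, and they are reported alongside the pooled one.

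**Conclusion.** The point holds in a limited, conditional form. As written, the plan permits a pooled amyloid contrast that ignores one of its two enrolment factors. That contrast is confounded only if the DLB shares differ between the amyloid groups, which is likely to some degree, and if DLB and PDD differ in response given baseline, which is unknown.

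With cells kept at 6 to 8 the bias is at most about 4 points at an assumed difference of 30, against a CI half-width near 48. A layout such as 8/5/5/7 gives 6 to 12 points at differences of 30 to 60. That is a noticeable part of the 30-point difference of interest but well inside the interval. With equal cells the cost is only a reported interval about 3% wider than the four-level model gives at 30 points (52.7/51.3) and about 13% wider at 60 (57.8/51.3).

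The figures assume SD 60 as the residual SD and a diagnosis effect that is the same in both amyloid groups. The importance is minor: the comparison is secondary, and the plan does not expect statistical significance.

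**What to change.** In SAP 5.5.2, state one ANCOVA for percentage change in CSF cGMP with the four-level diagnosis-by-amyloid factor and baseline cGMP. Derive all five comparisons from it as contrasts, and define the pooled amyloid effect as the simple average of the within-DLB and within-PDD differences. Cross-refer from SAP 5.3.2 and 5.3.4 so that the combined groups are not read as a separate two-group model.

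The cost is wording plus 2 error df in the pooled comparison (1 if diagnosis is added as a single term). If diagnosis has no effect, the pooled CI widens by 0.6% at 6/6/6/6 (51.3 versus 50.9), 1.5% at 6/8/8/6 (47.4 versus 46.7) and 2.7% at 8/5/5/7 (51.1 versus 49.8). It widens by about 7% at 8/8/4/4 (54.4 versus 50.9), where equal weighting of the two diagnoses is inefficient. The model also assumes a common residual variance and a common baseline slope across the four subgroups, which the SAP should say.

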A predose plasma sample will be collected at the study visit after 9 weeks on E2027. It will be assayed for plasma biomarkers related to DLB or PDD or E2027 PD effects on these biomarkers if appropriate. Plasma concentrations of A β 42 and A β 40 will be measured by the validated immunoprecipitation LC-MS/MS C2N Preclivity plasma assay. Plasma concentrations of p-tau 181, GFAP, and NFL will be measured by Quanterix Simoa plasma assay.

Pharmacogenomic Assessments

Blood samples will be collected as specified in the Schedule of Procedures/Assessments (Table 5) where feasible and in accordance with local regulations. Participation in PGx assessments is voluntary and subjects must provide a separate informed consent before blood collection for PGx assessments.

The PGx blood samples may be used to genotype common and rare genetic variants (including apolipoprotein E [ApoE] genotype). Data obtained from the PGx analysis will be used for research, to assist in developing safer and more effective treatments and will not be used to change the diagnosis of the subject or alter the therapy of the subject. The deoxyribonucleic acid (DNA) will not be used to determine or predict risks for diseases that an individual subject does not currently have. Any sample may be stored for up to 15 years, based on country specific regulations to assist in any scientific research questions related to E2027 or DLB or PDD.

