5.1.3 Exploratory Endpoints

- The following clinical efficacy endpoints at 12 weeks of treatment
 - Change from baseline in MoCA total score
 - Change from baseline in WAIS-IV DSC score
 - CIBIC-Plus scale
 - CGIC scale
 - Change from baseline in CFI score
 - Change from baseline in MMSE total score
 - Change from baseline in NPI total score, subscores and caregiver distress score
 - Change from baseline in SAPS-PD total score
 - Change from baseline in FAQ total score
- Change from baseline in CSF cGMP at 9 weeks of treatment
- Percentage change and change from baseline at 9 weeks of treatment in other biomarkers in CSF and/or plasma, including using other diagnostic subgroups classifications based on baseline biomarkers (if appropriate)
- PK of E2027 in subjects with DLB or PDD, using population modelling
- Relationships between E2027 in plasma/CSF and its effects on the following variables using PK/PD modelling, if data permit:
 - Plasma/CSF PD biomarkers (including CSF cGMP),
 - Clinical efficacy (including MoCA, WAIS-IV DSC, CIBIC-Plus, NPI, MMSE, CFI, SAPS-PD, FAQ, and CGIC at 12 weeks of treatment),
 - Safety variables
- Relationships of the plasma and CSF PD biomarkers compared to MoCA, WAIS-IV DSC, CIBIC-Plus, NPI, MMSE, CFI, SAPS-PD, FAQ, and CGIC at 12 weeks of treatment, if data permit
- Relationships amongst plasma biomarkers and CSF biomarkers at baseline and after treatment (if appropriate)
- Subgroup analyses based on genotype classification for CSF cGMP changes from baseline and clinical endpoints

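### For the amyloid and tau markers that define their own subgroup, the SAP's unadjusted tables of Week 9 change are confounded by regression to the mean

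*SAP*

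**What the plan says.** SAP 5.5.2 sends Week 9 biomarker results into the subgroups without qualification: "both percentage change and change from baseline at 9 weeks) will be summarized by subgroups, as defined in section 5.3.4". SAP 5.1.3 makes this an exploratory endpoint, "including using other diagnostic subgroups classifications based on baseline biomarkers".

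SAP 5.3.4 defines two layers of subgroup.

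- **Primary grouping:** with or without amyloid copathology, cut on plasma Aβ42/40 at 0.092, within DLB and PDD and combined. It applies to all data.
- **Alternative groupings:** among others "Plasma p-tau181 (<2.2" and "CSF p-tau181 (<52.8", plus CSF Aβ42/40, plasma and CSF p-tau181/Aβ42 and CSF total tau/Aβ42. One is a genotype: "Genotype classification (ApoE4 positive or negative), by DLB, PDD and Overall". Their reach is limited: "The demography, MoCA and some of the PD endpoints will be presented by the subgrouping as column headers instead of the amyloid copathology". The PD endpoints meant are not named.

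Formal modelling of the other biomarkers is optional. After CSF amyloid, the list in SAP 5.5.2 runs "plasma p-tau181, CSF p-tau181, plasma neurogranin, plasma neurofilament, CSF neurogranin, CSF neurofilament, etc) may be analyzed similarly, if appropriate". SAP 5.3.2 requires the variable's own baseline as a covariate in any model, but that rule does not reach descriptive summaries.

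Plasma Aβ42 and Aβ40 are measured again at Week 9, and so are the other plasma markers: "Plasma concentrations of p-tau 181, GFAP, and NFL will be measured by Quanterix Simoa plasma assay" (Protocol 9.5.1.3.2). CSF markers other than cGMP may be assayed if appropriate.

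**The concern.** Protocol Table 6 plans one plasma biomarker sample and one CSF sample before treatment and one of each on treatment. SAP 8.2.2 takes the last pretreatment value as baseline. For a marker that defines its own subgroup, the reading that places a subject in the low or high group is therefore also the reading subtracted to obtain the change. A subject whose reading was high partly by chance is placed in the high group and then tends to fall on re-measurement. The low group does the reverse.

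Nothing in the plan separates this from a drug effect. The study has a single arm (Protocol 9.4.3), there is no repeat baseline, and the only caution in SAP 5.3.4 concerns small subgroups. A table showing p-tau181 falling in the high p-tau181 group and rising in the low group could be taken for a status-specific effect of E2027, which is the kind of finding the exploratory endpoint looks for.

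**Working it through.** **The plan's own figures.** The documents give no figure for regression to the mean. The sample-size section (SAP 4) concerns cGMP and is used here only for numbers. It reproduces: SE = 60 × √(2/6) = 34.64, and the normal probabilities of an observed difference of at least 30 are 97.8%, 80.7% and 28.2% for true differences of 100, 60 and 10. Six completers per subgroup means 12 per diagnosis and 24 overall.

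**Inputs**

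- Cut position: taken at the median. For plasma Aβ42/40 in DLB this fits Protocol 7.2, where the 0.092 cut split Study 201 into 57 and 56 subjects. For the other markers it is an assumption.
- Test-retest correlation ρ over the interval: not in the documents, so a range is shown.
- Baseline and Week 9 values: bivariate normal with equal variance and no true change (assumed).

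**Formula.** Expected change in a group = −(1 − ρ) × (group baseline mean − overall mean). A median cut puts the group means at ±√(2/π) = ±0.798 SD, so the gap (low minus high) is (1 − ρ) × 1.596 SD.

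| ρ (assumed) | Low group | High group | Gap |
|---|---|---|---|
| 0.6 | +0.32 SD | −0.32 SD | 0.64 SD |
| 0.7 | +0.24 | −0.24 | 0.48 |
| 0.8 | +0.16 | −0.16 | 0.32 |
| 0.9 | +0.08 | −0.08 | 0.16 |
| 0.95 | +0.04 | −0.04 | 0.08 |

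A cut at the 30th or 70th percentile changes the gap little (0.33 SD at ρ = 0.8).

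**Percentage change.** With lognormal values, an assumed CV of 40% and ρ = 0.8, the low group averages +9.3%, the high group −3.3% and all subjects +3.0%, again with no drug effect.

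**Components of a ratio.** This covers plasma Aβ42 or Aβ40 change tabulated by the plasma Aβ42/40 cut. If the two log components are independent and equally variable, each correlates 1/√2 = 0.707 in size with the log ratio. The gap is then (1 − ρ) × 0.707 × 1.596, or 0.45, 0.23 and 0.11 SD at ρ = 0.6, 0.8 and 0.9.

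**Grouping by a different marker** (simulation, ρ = 0.8). The low and high groups move by ±0.00, ±0.05 and ±0.10 SD when the grouping marker's baseline correlation with the changing marker is 0, 0.3 and 0.6, against ±0.16 SD for a self-cut. This model lets the grouping marker share the chance part of the baseline reading. Plasma and CSF come from separate samples and are run on different assays (Protocol 9.1.1.1 and 9.5.1.3.2), so it is probably pessimistic for grouping by the other fluid.

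**Baseline adjustment** (simulation, 24 subjects, ρ = 0.8). The group difference, high minus low, goes from −0.32 SD to about 0. Its SE rises from 0.26 to 0.43 SD because the group is a function of the covariate.

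**The case against.** **These tables may not all exist.** SAP 5.3.4 restricts the alternative groupings to some PD endpoints, the protocol says as appropriate, and the table shells are a separate document (SAP 11). This stands for the alternative groupings: a reader might infer that every marker is tabulated by its own cut, and the text does not establish that. It does not dispose of the point. The restriction does not exclude self-cut pairs, SAP 5.5.2 has no such limit, and the primary grouping, itself a plasma Aβ42/40 cut, applies to all data.

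**The outputs are descriptive.** A reader might infer an inflated false-positive rate. Under no drug effect, an unadjusted two-sample test on change at ρ = 0.6, 0.8 and 0.9 would give p < 0.05 in about 40%, 22% and 13% of trials with 24 subjects, or 20%, 12% and 8% with 12. The SAP plans no such test. Its descriptive summaries are mean, SD, median, minimum, maximum and n (SAP 5), and confidence intervals for subgroup differences come with the baseline-adjusted ANCOVA. Those rates describe no planned output.

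**The pattern need not appear.** It holds in expectation. For ρ from 0.5 to 0.95, the simulated chance that the low mean rises and the high mean falls is 0.73 down to 0.39 with 12 subjects and 0.87 down to 0.45 with 24.

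**The size is unknown.** Besides ρ, it depends on the distribution. If a marker is bimodal with the cut between modes at ±0.9 SD (an assumption), the gap at ρ = 0.9 is about 0.04 SD, not 0.16. This stands.

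**Phase 3 selection.** A reader might infer that these tables would steer it. Protocol 7.3 does mention biomarker-defined characteristics, but the inference it sets out rests on CSF cGMP and its association with efficacy, and cGMP is not self-cut.

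**Conclusion.** The point holds for a limited set of markers: plasma Aβ42/40 and its components under the primary grouping; and, where the alternative tables are produced, plasma and CSF p-tau181, CSF Aβ42/40, the p-tau181/Aβ42 ratios and CSF total tau/Aβ42. For these, unadjusted Week 9 change by subgroup carries a built-in expected gap of roughly 0.16 to 0.64 SD for an assumed ρ of 0.9 to 0.6 and a median cut. The direction needs only ρ below 1 and a cut inside the distribution. The size rests on ρ, the normal model and the cut position.

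It would be wrong to extend this to every biomarker. CSF cGMP, neurofilament, neurogranin and GFAP have no cut on their own baseline in SAP 5.3.4, and ApoE4 is a genotype. The primary, secondary and safety analyses are untouched. Severity is minor: it concerns exploratory tables only, but the bias is known and cheap to avoid.

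**What to change.** Add a sentence to SAP 5.5.2, cross-referenced from 5.3.4, that applies only where a marker's change would be tabulated by a subgroup cut on that marker's own baseline or on a ratio containing it. For those pairs, any statement about change should rest on one of two outputs:

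- a grouping by the other fluid: CSF-defined status for plasma change, plasma-defined status for CSF change;
- an estimate adjusted for the marker's continuous baseline.

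If the unadjusted self-cut table is kept for the primary subgroups, so that the commitment to show all data by those groups is met, label it as subject to regression to the mean and not as evidence of a status-specific drug effect. All other marker-by-subgroup tables stay as planned.

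The cost is one sentence and a few table shells, with no new data. The adjusted group contrast is less precise (SE 0.43 against 0.26 SD in the 24-subject example). Grouping by the other fluid reduces the bias but need not remove all of it if the chance variation in the two fluids is correlated.
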